1.0 Objectives*

Two-thirds of the US population, particularly African Americans (AA), is at risk for inadequate or deficient 25-hydroxy-vitamin D (25(OH)VD). Epidemiological studies demonstrate an association between better health outcomes and higher blood levels of 25(OH)VD. Randomized controlled clinical trials have shown that, while supraphysiological high doses of VD are needed to achieve adequate blood levels of 25(OH)VD, not all subjects respond to them. Recent studies have also questioned the therapeutic effects of high-dose VD supplementation. This application presents our design for a randomized, double-blind, placebo-controlled clinical trial to test the hypothesis that supplementation with VD in combination with L-cysteine (LC) is more successful at optimizing the statuses of 25(OH)VD [biological signatures] and simultaneously decreasing TNF- α and IR [functional or clinical outcomes], suggesting a better therapeutic approach compared with supplementation with VD alone in AA subjects.

2.0 Background*

Previous human studies report that VD supplementation increases circulating 25(OH)VD status but has limited success in reducing insulin resistance (IR). Other human studies report that supplementation with LC lowers TNF- α and IR. This clinical trial will determine the impact of combined supplementation with VD+LC on increases in levels of 25(OH)VD as well as simultaneous reduction in TNF- α and IR biomarkers (mediators of clinical benefit) in the AA population. The mechanistic focus of this clinical trial will determine whether combined supplementation with VD and LC provides a more successful approach to increasing 25(OH)VD [biological signatures] as well as simultaneously decreasing TNF- α and IR [functional or clinical outcomes], compared with supplementation with VD alone. If the results are positive, future studies will investigate potential of this approach to reduce the inflammation, pain, and other health issues among AA in a full-scale efficacy trial.

3.0 Inclusion and Exclusion Criteria*

Informed written consent will be obtained from all subjects according to the IRB approved protocol. All subjects in this study will be adult AA volunteers and will meet the inclusion/exclusion criteria given below.

INCLUSION CRITERIA: (1) African-American adults aged 18-65 years willing to participate in 5 clinic visits where blood will be drawn; (2) participants who demonstrate an understanding of the risks and benefits of the protocol and sign the informed consent form; (3) participants willing to complete standard health history questionnaire before and during the study (**Copy enclosed**); (4) women with negative pregnancy tests (pregnancy test will be performed on all women participants)

EXCLUSION CRITERIA: (1) History of cardiovascular disease, sickle cell disease, or metabolic disorders including: diabetes, uncontrolled hypertension, hypothyroid, or hyperthyroid; (2) any sign of hepatic dysfunction or renal dysfunction, hypercalcemia, or nephrolithiasis; (3) those taking antiepileptic medications, glucocorticoids, or weight loss or other dietary supplements within the two months previous to enrollment or during the study; (4) those who visit tanning booths; (5) any subject who develops an infection and has to take antibiotics; and (6) women with positive pregnancy tests or those who are nursing. (7) adults unable to consent or prisoners. Any subject taking vitamin D or any other vitamin

PROTOCOL TITLE: Optimization of 25(OH) vitamin D levels in African Americans

or herbal supplement even advised by a doctor or over-the-counter will not be enrolled in the study.

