5.0 Multi-Site Research* N/A (This is only site)

6.0 Study Timelines*

Potential subjects will be contacted over phone or potential subjects may call in response to advertisement and agrees to participate in this study will be asked to come to the clinic after fasting overnight. Fasting blood will be collected after written informed consent. Blood collected at V₋₁ will serve as the sample for the screening visit for the clinical trial. Subjects meeting the inclusion/ exclusion criteria will continue in the clinical trial. All subjects will fill out the complete standard health history before the study and at each visit during the study. This clinical trial will be registered at the ClinTrial.gov site.

Initially, all of the study subjects will be provided placebo supplementation as a placebo run-in period for one month before randomization. Visit 2 (V₀) is for obtaining baseline levels after the run-in period. AA-subjects will be block randomized into four groups. Members of the groups will ingest capsules containing placebo and supplements, orally, daily: (I) placebo (P); (II) LC (1000 mg); (III) VD (2000 IU); (IV) VD and LC. Each capsule will contain a placebo or cholecalciferol (2000 IU) or LC (1000 mg). Placebo group will take two placebo capsules a day in the morning; II LC group will receive two capsules of LC daily; (III) VD group will take two capsules and each capsule will contain 1000 IU VD daily; (IV) VD+LC group will take daily two capsule containing 1000 IU+500 mg LC. Supplements will be taken daily with food at breakfast for 6 months, while participants continue to carry on a normal lifestyle. During the placebo run-in period, all subjects will also take two placebo capsules daily. Based on previous experience, we expect a dropout rate of about 16% as a result of non-compliance, lost contact, taking another medicine, or a subject found to have another disorder. We expect that at least 30 subjects in each group will complete the study. Overnight fasting blood will be collected at each visit. Also, anthropomorphic data, body weight, and height (BMI), the record of any drug use, any adverse effects/complaints (related or unrelated), and Questionnaire will be collected at each visit by the nurse. It is likely to require ~90 minutes to collect the subject's history and other data in interviews with the nurse/dietician and investigators.

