7.0 Study Endpoints*

PROTOCOL TITLE: Optimization of 25(OH) vitamin D levels in African Americans

Primary Endpoints: Blood levels of 25(OH)VD, TNF- α , and HOMA-IR.

Safety Endpoints: Serum calcium (Ca²⁺), PTH, liver, and kidney function tests will be carried out at visits 0, 2, 4, and 6. Whole blood CBC and pregnancy tests will be done at all visits.

Secondary Endpoints: Blood levels of 1,25(OH)₂VD, HbA_{1c}, and pro-inflammatory and anti-inflammatory cytokines (such as IL-2, IL-6, and IL-10).

We will also perform tests to monitor liver and kidney function tests at each visit and complete blood count analyses for any sign of any anemia or unexpected changes in white or red blood cell profiles.

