12.0 Withdrawal of Subjects*

Subjects found to be consuming over the counter supplement, positive pregnancy tests or not able to follow the instructions will be withdrawn from the study. Any data collected on subject withdrawn from the study will not be used in any analyses. The investigator will ask a subject who is withdrawing whether the subject wishes to provide further data collection from routine medical care.

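### Section 12.0 bars all data of withdrawn subjects from every analysis, although its withdrawal grounds can arise after randomization

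*Protocol*

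**What the plan says.** Section 12.0 of the protocol sets the withdrawal rule: "Subjects found to be consuming over the counter supplement, positive pregnancy tests or not able to follow the instructions will be withdrawn". The next sentence fixes what happens to their data: "Any data collected on subject withdrawn from the study will not be used in any analyses". It makes no exception for values measured before the withdrawal, or for safety data.

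Two of these three grounds also appear among the exclusions in 3.0. Item 3 excludes "those taking antiepileptic medications, glucocorticoids, or weight loss or other dietary supplements within the two months previous to enrollment or during the study", so it reaches past entry. Item 6 excludes pregnant women, and 7.0 adds "Whole blood CBC and pregnancy tests will be done at all visits". Item 5 of 3.0 excludes "any subject who develops an infection and has to take antibiotics" and gives no time window. Infection, antibiotics, glucocorticoids and antiepileptics are not named in 12.0.

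Under 6.0, randomization follows a one-month placebo run-in, and supplements are then taken for 6 months. The same section expects about 16% dropout from "non-compliance, lost contact, taking another medicine, or a subject found to have another disorder". Section 10.0 describes that 16% as also covering screen failures and withdrawals before randomization.

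**The concern.** The trial is a randomized, double-blind comparison of four arms. Randomization makes the arms comparable at V0. That holds in the analysis only if membership of the analysed groups does not depend on what happens afterwards. A rule that deletes a randomized subject because of supplement use, a pregnancy or failure to follow instructions during treatment makes it depend on exactly that. Ability to follow instructions, for example, could differ between arms if one of the capsules is less well tolerated.

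Two kinds of usable information are lost. One is the efficacy values measured before the event, which the event cannot have affected. The other is safety: read literally, a ban covering all analyses takes in the calcium, PTH, liver and kidney results that 7.0 lists as safety endpoints, so any summary by arm would omit the withdrawn subjects.

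**Working it through.** **Can the grounds arise after randomization?**

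| Ground in 12.0 | Link to 3.0 | Possible after randomization? |
|---|---|---|
| Over-the-counter supplement | Item 3, which runs on during the study | Yes, explicit |
| Positive pregnancy test | Item 6; tested at all visits (7.0) | Yes, explicit |
| Not able to follow instructions | None | Yes; it has no time limit and treatment lasts 6 months |

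For these three, withdrawal and the data ban both stand in the text. Withdrawals during the run-in month do not harm the randomized comparison; those in the following 6 months can.

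**Infection and listed drugs.** Items 3 and 5 of 3.0 can also be met after randomization as worded. The step from meeting them to being withdrawn is not written anywhere. Without that step the data ban in 12.0 does not apply.

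**What the ban discards.** Inputs: three primary endpoints (7.0) and four time points (10.0). Assumption: the four time points are V0, V2, V4 and V6, with all three primary endpoints measured at each. Section 7.0 says of the safety chemistry that it "will be carried out at visits 0, 2, 4, and 6", and the 5 clinic visits in 3.0 less the screening visit leave 4, so the assumption fits the text.

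Primary values collected before the event = 3 × number of visits already made:

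- event between V0 and V2: 3 × 1 = 3
- event between V2 and V4: 3 × 2 = 6
- event between V4 and V6: 3 × 3 = 9

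Any draw at the visit where the event comes to light is discarded as well.

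**How many subjects?** The document gives no rate for supplement use, pregnancy, failure to follow instructions, infection or drug use. The only figure is the all-cause loss: 0.16 × 160 = 25.6 subjects. Because 10.0 mixes losses before and after randomization, the loss per arm after randomization lies between 0 (all before) and 25.6 / 4 = 6.4 of 160 / 4 = 40 (all after).

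**The plan's own figure.** Section 10.0 says that 160 enrolled gives more than 30 completers per arm. 160 × (1 − 0.16) = 134.4, and 134.4 / 4 = 33.6 per arm. The statement reproduces. The margin over the 27 that 10.0 requires for IR is 33.6 − 27 = 6.6, or 30 − 27 = 3 at the stated goal of 30.

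**Bias.** With no event rates by arm and no SD for any endpoint, neither its size nor its direction can be computed.

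**The case against.** The strongest counter-argument concerns infection and prescribed drugs. A reader might infer from items 3 and 5 that a randomized subject who needs antibiotics or a glucocorticoid is withdrawn and loses all data. Some text points that way: 6.0 counts taking another medicine as a dropout reason, and 12.0 enforces other exclusions after entry. But the documents do not support it as a statement of the plan. Section 12.0 names three grounds and these are not among them, which may be deliberate. The 16% includes losses before randomization. Section 6.0 applies the criteria at screening, and item 5 has a natural meaning in the run-in month. This objection stands, so that part remains conditional.

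A reader might also infer that each withdrawal costs a full series of 3 × 4 = 12 primary values. That overstates the effect of the data sentence. A withdrawn subject stops attending, so later draws are never taken; the rule discards only what was already collected.

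A third argument is that removing disturbed biomarker draws is defensible in a trial with TNF-alpha as a primary endpoint and a mechanistic focus (2.0). That can justify setting aside particular draws in a supporting analysis. It does not justify deleting the baseline and earlier draws of the same subject, or the safety results.

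On safety, the protocol describes no between-arm safety analysis. It records "any adverse effects/complaints (related or unrelated" at each visit (6.0), and the monitoring committee reviews laboratory reports and meets on reported side effects (11.0). Individual events are therefore not hidden; the loss is confined to summaries by arm.

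Finally, analysis sets are often left to the SAP. Here the protocol does not leave the matter open: it states a total ban, and an SAP that kept the data would contradict it.

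**Conclusion.** The point holds for the three grounds that 12.0 names. As written, the rule removes randomized subjects because of events after randomization and discards their earlier efficacy values and their safety data. For infections needing antibiotics and for the listed drugs it holds only if such subjects are withdrawn, which the document leaves unstated.

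In data terms, 3, 6 or 9 primary values collected before the event are discarded per affected subject, under the visit assumption above. The number of affected subjects is unknown, and the size and direction of bias cannot be computed. A power shortfall might be inferred, but the figures do not show one: the planned loss still leaves 33.6 completers per arm against 27 required. The rule should be changed because it is explicit and cheap to correct, not because a particular harm has been shown. Confidence is medium.

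**What to change.** 1. In 12.0, replace the data sentence with: *Data collected on any randomized subject, whatever the reason for withdrawal, are kept in the efficacy and safety analyses in the randomized arm.* This covers the three named grounds and needs no decision about infections or drugs. It keeps what was collected; it does not add visits after withdrawal.
2. In 3.0, state that item 5 and the drug part of item 3 apply only up to randomization, including the run-in month. After that, record infections as adverse events and antibiotics, glucocorticoids or antiepileptics as concomitant medication. Whether capsules continue during an illness or a pregnancy remains a clinical decision.
3. Optionally, add a sensitivity analysis that omits draws taken during an infection or while on a listed drug. Draws taken before the event stay in.

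The cost is amendment wording in two sections and, if chosen, one further analysis. Visits, blood draws and the record of drug use are already planned. The downside is that some off-protocol or disturbed values stay in the main analysis and add noise; the optional analysis would show how much of it comes from infections and listed drugs.

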4.0 Study-Wide Number of Subjects*

This is the only site for enrollment and will enroll 160 subjects.

5.0 Multi-Site Research* N/A (This is only site)

6.0 Study Timelines*

Potential subjects will be contacted over phone or potential subjects may call in response to advertisement and agrees to participate in this study will be asked to come to the clinic after fasting overnight. Fasting blood will be collected after written informed consent. Blood collected at V₋₁ will serve as the sample for the screening visit for the clinical trial. Subjects meeting the inclusion/ exclusion criteria will continue in the clinical trial. All subjects will fill out the complete standard health history before the study and at each visit during the study. This clinical trial will be registered at the ClinTrial.gov site.

Initially, all of the study subjects will be provided placebo supplementation as a placebo run-in period for one month before randomization. Visit 2 (V₀) is for obtaining baseline levels after the run-in period. AA-subjects will be block randomized into four groups. Members of the groups will ingest capsules containing placebo and supplements, orally, daily: (I) placebo (P); (II) LC (1000 mg); (III) VD (2000 IU); (IV) VD and LC. Each capsule will contain a placebo or cholecalciferol (2000 IU) or LC (1000 mg). Placebo group will take two placebo capsules a day in the morning; II LC group will receive two capsules of LC daily; (III) VD group will take two capsules and each capsule will contain 1000 IU VD daily; (IV) VD+LC group will take daily two capsule containing 1000 IU+500 mg LC. Supplements will be taken daily with food at breakfast for 6 months, while participants continue to carry on a normal lifestyle. During the placebo run-in period, all subjects will also take two placebo capsules daily. Based on previous experience, we expect a dropout rate of about 16% as a result of non-compliance, lost contact, taking another medicine, or a subject found to have another disorder. We expect that at least 30 subjects in each group will complete the study. Overnight fasting blood will be collected at each visit. Also, anthropomorphic data, body weight, and height (BMI), the record of any drug use, any adverse effects/complaints (related or unrelated), and Questionnaire will be collected at each visit by the nurse. It is likely to require ~90 minutes to collect the subject's history and other data in interviews with the nurse/dietician and investigators.

The placebo run-in period is meant to stabilize subjects in the study and will prevent any effect due solely to inclusion in the study. Placebo and supplement capsules will be similar in appearance, taste, texture, and smell, and will be provided by the [name]/pharmacist, who will have the codes for which subjects are assigned to which supplement or placebo. Both subjects and investigators will be blinded to the supplement each subject will receive. [name] will randomize the subjects. Documentation about capsules/supplements to be used is enclosed on last page (page 9) of this protocol.

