28.0 Drugs or Devices

This research involves dispensing micronutrient supplements vitamin D and L-cysteine. These are also sold over the counter in any discount store. These nutrients are normal part of our food consumed by the public, such as milk, cheese, eggs and green vegetables. The supplement capsules will be provided by the investigators free of any cost to the participants.

Capsules details.

1. The study subjects will ingest capsules containing placebo and supplements, orally, daily: (I) placebo (P); (II) L-cysteine (LC) (1000 mg); (III) Vitamin D (VD) (2000 IU); (IV) VD+LC groups
2. To start with each group/subject will have placebo run-in period for one month and all subjects will take two placebo capsules daily.
3. After one month of Placebo run-in period, all subjects will be randomized into four groups. Each capsule will contain a placebo or cholecalciferol (2000 IU) or LC (1000 mg) or VD+LC. Supplements will be taken daily with food at breakfast for 6 months.
4. Placebo group will take two placebo capsules a day in the morning; II LC group will receive two capsule of LC (500 mg each) daily; (III) VD group will take two capsule of VD (1000 IU) daily; (IV) VD+LC group will take daily two capsule of combination (VD 1000 IU VD+ 500 mg LC) daily.
5. Supplements will be taken daily with food at breakfast for 6 months.
6. We are working with Company named: Superior Supplement Manufacturing, Fountain Valley California, to get these capsules made. These capsules will look similar and will be of similar size.

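### The general statement of capsule strength, at two capsules a day, gives twice the listed daily dose in the VD and LC arms and contradicts the strengths given arm by arm

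*Protocol*

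**What the plan says.** Section 6.0 lists the daily regimens of the active arms as "II) LC (1000 mg); (III) VD (2000 IU); (IV) VD and LC". The next sentence gives a strength for every capsule: "Each capsule will contain a placebo or cholecalciferol (2000 IU) or LC (1000 mg". The arm-by-arm instructions follow:

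- LC arm: "II LC group will receive two capsules of LC daily", with no strength given.
- VD arm: "VD group will take two capsules and each capsule will contain 1000 IU VD daily".
- Combination arm: "VD+LC group will take daily two capsule containing 1000 IU+500 mg LC".

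Section 6.0 then refers the reader elsewhere for the capsules: "Documentation about capsules/supplements to be used is enclosed on last page (page 9) of this protocol". That appears to mean the numbered list in section 28.0. Item 1 of the list gives the same daily doses, "II) L-cysteine (LC) (1000 mg); (III) Vitamin D (VD) (2000 IU); (IV) VD+LC groups". Item 3 carries the general sentence again, with the combination added but no strengths for it: "Each capsule will contain a placebo or cholecalciferol (2000 IU) or LC (1000 mg) or VD+LC". Item 4 gives two capsules a day in every arm, at 500 mg per LC capsule, 1000 IU per VD capsule, and 1000 IU plus 500 mg for the combination capsule.

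**The concern.** The same capsule has two strengths. A VD capsule is 2000 IU in one sentence and 1000 IU in another, within section 6.0 and again within section 28.0. An LC capsule is 1000 mg in the general sentence and 500 mg in section 28.0 item 4. Section 6.0 gives no arm-specific strength for the LC arm, so a reader of that section alone has only the general 1000 mg to apply to two capsules.

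Capsule content defines the intervention. Section 28.0 item 6 describes the capsules as still being arranged with a manufacturer, so this text could feed into the specification. Subjects and investigators are blinded and the capsules look alike, so a wrong strength would not be apparent to them.

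The objective in section 1.0 is to compare VD plus LC with VD alone. If the VD capsules followed the general sentence, the comparator would carry twice the vitamin D of the combination arm, and 25(OH)VD is a primary endpoint. The LC arm is the more exposed to misreading, because its strength is missing from section 6.0. Section 11.0 also bases its minimal-risk statement on the dose used, which the protocol does not state in one way only.

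**Working it through.** Daily dose = capsules per day x content per capsule. Both sections give two capsules a day in every arm.

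**Step 1. Reproduce the listed doses from the arm-specific strengths.**
- VD: 2 x 1000 IU = 2000 IU; listed 2000 IU; ratio 1.0 (strength in sections 6.0 and 28.0 item 4).
- LC: 2 x 500 mg = 1000 mg; listed 1000 mg; ratio 1.0 (strength in section 28.0 item 4 only).

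**Step 2. Apply the general sentence (section 6.0; section 28.0 item 3).**
- VD: 2 x 2000 IU = 4000 IU; 4000 / 2000 = 2.0 times the listed dose.
- LC: 2 x 1000 mg = 2000 mg; 2000 / 1000 = 2.0 times the listed dose.

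**Step 3. Compare each single-agent arm with the combination arm.** Neither section states a numerical daily total for the combination arm. Taking 1000 IU plus 500 mg as the content of one capsule, the total is 2 x 1000 = 2000 IU and 2 x 500 = 1000 mg.

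| Component | Text followed for the single-agent arm | Single-agent arm, per day | Combination arm, per day | Ratio |
|---|---|---|---|---|
| LC | Listed dose, or section 28.0 item 4 | 1000 mg | 1000 mg | 1.0 |
| LC | General sentence | 2000 mg | 1000 mg | 2.0 |
| VD | Listed dose, or arm-specific strength | 2000 IU | 2000 IU | 1.0 |
| VD | General sentence | 4000 IU | 2000 IU | 2.0 |

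Section 6.0 does not say outright that the combination strengths are per capsule. If they were the total for the two capsules, the combination arm would receive 1000 IU and 500 mg a day and every ratio in the table would double. Steps 1 and 2 do not depend on this assumption.

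**Step 4. Test whether another reading reconciles the text.** One active plus one placebo capsule would give 2000 IU or 1000 mg a day from the general strengths and so match the listed doses. The arm-specific sentences exclude it: the LC arm takes two LC capsules, and each of the two VD capsules contains 1000 IU. The general figures may have been meant as daily totals, but the sentence assigns them to each capsule, in both sections.

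**The case against.** The best defence is that the protocol nearly settles the point itself. Section 28.0 item 4 gives a capsule count and strengths for every active arm, and for the single-agent arms these reproduce the listed daily doses exactly. Section 6.0 repeats the arm-specific strengths for VD and for the combination. Against them stands one general sentence, appearing twice and each time followed closely by the arm-specific text. To reach the doubled dose a reader must set aside several consistent statements. The 2.0 ratio for LC mixes the general sentence for one arm with the arm-specific strength for another. On this view the matter is a wording slip with a hypothetical consequence, since the capsules are made to order and supplied by a pharmacist who holds the codes.

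Much of this stands. The arm-specific text is coherent, the contrast of VD plus LC with VD alone is balanced on it, and nothing shows that anyone used the general sentence to make or dispense capsules. The fault is an inconsistency of wording, and the design itself is not in question. The contradiction remains all the same: the list that ought to settle the matter carries the conflicting sentence in item 3, and no rule of precedence is given. The sentence is also operative text about what subjects take.

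**Conclusion.** The concern holds. Sections 6.0 and 28.0 each state capsule contents that cannot all be true. The general sentence gives 4000 IU or 2000 mg a day, 2.0 times the listed 2000 IU and 1000 mg; the arm-specific strengths give 1.0 times. The doubling depends only on two supplement capsules a day, which both sections state. The comparison with the combination arm depends in addition on reading its strengths as per capsule.

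The conclusion is limited to the text. On all arm-specific wording the main contrast is balanced, and the protocol does not show what was manufactured or dispensed, so no dose imbalance is demonstrated. Because the conflict concerns the content of the assigned intervention, it must be corrected. Which figures are right is for the sponsor to determine.

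**What to change.** Reconcile section 6.0 with section 28.0 items 1, 3 and 4. For each of the four arms, state the content of one capsule, the number of capsules per day and the resulting daily total, so that the three agree and read the same in both sections. A short table that both sections cite would do. Include the LC capsule strength, which section 6.0 lacks for the LC arm, and the daily totals for the combination arm, which neither section states. Check the reconciled text against the manufacturer's specification and the pharmacist's dispensing record. The sponsor chooses the figures.

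The cost is a wording change in two sections and one check against existing records. The design, sample size and visits do not change.

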10.0 Data Management* and Confidentiality

Analyses of data will be performed by the biostatistician, [name]. A *p*-value of less than 0.05 for a statistical test will be considered significant. Data will be analyzed statistically to compare the 4 groups at baseline and various visits using ANOVA. The Wilcoxon signed-rank or paired *t*-test will be used to determine significant changes after supplementation for each treatment group, and the ANOVA test to compare the 4 treatment groups on changes. The results for the pairwise comparisons among the 4 time points will determine whether there is a significant change in the outcome variables over time. The effect of covariates or possible confounders (age, sex, BMI, initial levels of outcomes, etc.) will be controlled for and tested for their significant effects by including them in the repeated measures model used.

Based on animal studies, co-supplementation with LC+VD will be more successful and raise serum 25(OH)VD levels by nearly 30 ng/mL(17, 18). Our goal is to raise circulating 25(OH)VD levels by an average of 30 ng/mL, and reduce IR levels by 35% in all AA subjects receiving combined VD+LC supplementation. To observe a significant response or change, a sample size of 7 for 25(OH)VD, and 27 for IR were considered adequate using a paired *t*-test conducted at 5% level of significance and 80% power. We chose a goal of 30 subjects in each group who complete the study in the VD+LC supplementation and other groups. Based on our experience from a previously completed clinical trial (H-09-073), enrollment of and consent from 160 AA volunteers who participate in blood collection for screening should give us more than the required sample size of 30 subjects in each group (120 in 4 groups) after factoring in a dropout rate of about 16% for screen failures, withdrawal before randomization, or those who did not complete all the visits. Our experience also suggests that nearly 190 subjects will need to be contacted to achieve our goal of 160 AA volunteers who complete the written consent form and are enrolled in this clinical trial. This takes into account the fact that only about 85% of those initially contacted will indeed show up for the screening visit and complete the written informed consent.

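### The run-in cannot prevent participation or time effects after V0, and the within-arm tests, goals and sample size in Section 10.0 cannot separate such effects from the supplement

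*Protocol*

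**What the plan says.** Protocol Section 6.0 sets the order of events. First, "all of the study subjects will be provided placebo supplementation as a placebo run-in period for one month before randomization". Then "Visit 2 (V₀) is for obtaining baseline levels after the run-in period". Randomisation into four blinded groups follows ("AA-subjects will be block randomized into four groups"), one of them placebo, and treatment runs on from there: "Supplements will be taken daily with food at breakfast for 6 months, while participants continue to carry on a normal lifestyle". The purpose given for the run-in is: "The placebo run-in period is meant to stabilize subjects in the study and will prevent any effect due solely to inclusion in the study".

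Section 10.0 uses the data in two ways.

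- **Within arm.** A Wilcoxon signed-rank or paired t-test "will be used to determine significant changes after supplementation for each treatment group". The targets for VD+LC are also changes from the arm's own baseline: "Our goal is to raise circulating 25(OH)VD levels by an average of 30 ng/mL, and reduce IR levels by 35" per cent. The sample sizes of 7 for 25(OH)VD and 27 for IR rest on a paired t-test at the 5% level with 80% power.
- **Between arms.** The same sentence continues "and the ANOVA test to compare the 4 treatment groups on changes". A repeated measures model adjusts for age, sex, BMI and initial outcome levels.

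The hypothesis in Section 1.0 is comparative: VD+LC against VD alone.

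**The concern.** A run-in that finishes when the baseline is drawn can only move early effects of joining into that baseline. Section 6.0 describes exposures that continue afterwards: fasting visits, weighing, a questionnaire and health history each time, and long interviews with the nurse or dietician and investigators. Section 19.0 adds telephone calls and compliance follow-up. Season, diet and assay drift can also act over six months. None of this is prevented by what happened before V0.

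The within-arm tests, the two goals and the sample size all take change from own V0 as the response, and none subtracts the change on placebo. If participation or time moves IR or 25(OH)VD, an arm can show a significant change, or approach its goal, partly or wholly for that reason. The trial randomises a placebo group to remove exactly this.

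**Working it through.** **Inputs.** From Section 10.0: effects 30 ng/mL and 35%; n = 7 and 27; paired t-test, 5% level, 80% power; 30 completers per arm. The protocol gives neither an SD of change nor the sidedness of the test. I take the test as two-sided. The drift sizes are my assumptions.

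**1. The plan's own figures.** Without an SD, 7 and 27 cannot be reproduced forwards, only solved backwards. Paired t-test power comes from the noncentral t with n - 1 degrees of freedom and noncentrality d√n, where d = effect / SD of change. Setting power to 0.80:

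- 25(OH)VD, n = 7: d = 1.273, so SD = 30 / 1.273 = 23.6 ng/mL.
- IR, n = 27: d = 0.560, so SD = 35 / 0.560 = 62.5 percentage points.

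A one-sided reading gives SDs of about 28.1 ng/mL and 71.2 points.

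**2. Within-arm test with an inert supplement.** With 30 completers and a mean drift δ after V0, the noncentrality is (δ / SD) × √30.

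| Outcome | Assumed drift | δ / SD | Noncentrality | P(paired test significant) |
|---|---|---|---|---|
| IR | 5 points | 0.080 | 0.438 | 7.1% |
| IR | 10 points | 0.160 | 0.877 | 13.6% |
| IR | 15 points | 0.240 | 1.315 | 24.6% |
| 25(OH)VD | 5 ng/mL | 0.212 | 1.162 | 20.2% |
| 25(OH)VD | 10 ng/mL | 0.424 | 2.323 | 61.3% |

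The nominal rate is 5%. If the IR test is one-sided, with SD 71.2 and drift in the favourable direction, the three IR figures become 10%, 19% and 30%.

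**3. The planned between-arm comparison.** If every arm drifts by δ, the expected difference in change between two arms is (effect + δ) - (comparator effect + δ), and δ drops out. The ANOVA on changes is therefore protected against shared drift.

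**4. Cost of moving the inference there.** For two arms of 30, the SE of the difference in change is SD × √(2/30), against SD × √(1/30) for one arm. The ratio is √2, about 1.4, before V0 adjustment. For IR that is 62.5 × 0.258 = 16.1 points against 62.5 × 0.183 = 11.4. If the stated effects are read as net of a comparator, the two-sample noncentrality is d × √(30/2):

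- IR: 0.560 × 3.873 = 2.17, power about 57%. Reaching 80% needs 52 per arm (51 by the normal approximation).
- 25(OH)VD: 1.273 × 3.873 = 4.93, power above 99%. Reaching 80% needs 11 per arm.

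**The case against.** The strongest reply is that the design already holds the remedy. The ANOVA compares all four randomised, blinded groups on changes, the repeated measures model adjusts for initial levels, and shared drift cancels there. The paired test is also run in the placebo arm, so a participation effect would be visible. Which contrasts follow the ANOVA can properly be left to an SAP. All of this stands, and it limits the point to the within-arm tests, goals and sample size.

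A reader might infer that the trial as a whole credits participation effects to the supplement, or that the paired tests were chosen because of the run-in. The documents support neither. Section 10.0 never cites the run-in, its wording on changes after supplementation is temporal, and the paired tests would have the same limit if the sentence in 6.0 were absent.

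A reader might also add regression to the mean. Section 3.0 sets no entry threshold on 25(OH)VD, TNF-α or HOMA-IR, and screening uses the earlier sample, not V0. No shift in an arm's mean from that source is to be expected.

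Finally, the sentence speaks only of effects due solely to inclusion, not of time effects in general, and the drift sizes have no source in the protocol. Both are fair. But continued visits, interviews and calls are themselves consequences of inclusion, and they go on after V0, so the categorical claim still fails.

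**Conclusion.** The point holds in limited form. The sentence in 6.0 claims more than a one-month run-in ending at V0 can deliver. The own-baseline tests, goals and sample sizes in 10.0 cannot separate later participation or time effects from the supplement, although the planned ANOVA on changes can remove whatever is shared across arms.

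The size depends on drift that the protocol does not quantify. For IR, the inflation of the within-arm error rate runs from slight at 5 points to about fivefold at 15. These figures rest on the back-solved SD, a two-sided test, 30 completers and no supplement effect. They illustrate what could happen and do not predict that it will.

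**What to change.** **Section 6.0.** Delete the clause saying that the run-in will prevent any effect due solely to inclusion. State that the concurrent placebo arm controls for such effects.

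**Section 10.0.** Base claims of response on V0-adjusted between-arm differences in change, with 95% confidence intervals: each active arm against placebo, and VD+LC against VD alone, since that is the stated hypothesis. Keep paired and signed-rank results as descriptive.

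**Goals.** Either label +30 ng/mL and -35% as within-arm targets or restate them net of the comparator. If they are restated, say that with the back-solved SD and before V0 adjustment 30 per arm gives about 57% power for IR and over 99% for 25(OH)VD, and that the 80% figure belongs only to the within-arm test.

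**Cost.** Wording only, with no new data or subjects. The price is wider intervals (SE about 1.4 times that of an own-baseline change before V0 adjustment) and a less favourable stated power for IR. V0 adjustment should recover some precision, but the protocol gives no correlation from which to say how much.
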